The study team will first confirm eligibility and obtain approval from the treating clinician as described in the Recruitment and Enrollment section to contact the patient and discuss the study. Patients who are interested and verbally consent to the study will undergo a pre-screening questionnaire to determine eligibility. All study procedures can occur in-person, over the phone, or online via Zoom (a web-based, HIPAA-compliant video-conferencing platform associated with Columbia University Irving Medical Center). Participants will complete a screening questionnaire to collect demographics, contact information, and participant sleep quality and habits. Additional eligibility will be determined during the screening questionnaire. After completing the screening questionnaire, Phase B participants will be randomized to either the CC intervention arm or sleep hygiene education control group (in a 2:1 ratio). All participants will view two educational videos (~5 minutes each in length) that will provide information about the basics of sleep, the regulation of sleep (including aspects of how the external light environment impacts sleep), the relationship of sleep with health, function, and well-being and tips for achieving good sleep. Participants will have the option of watching the educational videos during hospitalization or at home for those with internet access and participants will also be given a written summary of the contents of the educational videos.

Phase B participants randomized to the active CC arm will then be instructed on how to administer the CC intervention. The CC intervention will consist of a wearable light visor to administer the BLT each morning for 30 minutes after awakening, and the BLB glasses to be worn each night from 8:00pm to bedtime. Instructions on how to use the intervention devices will be offered in person during enrollment, over the phone, or online via Zoom after the participant has returned home.

Visit 1/Baseline: After verbally agreeing to participate and enroll in the study, Phase B participants will be scheduled for Visit 1 (either in person, telephone, or video on Zoom). During Visit 1, participants will complete a questionnaire battery on their sleep, PTSD symptoms, and cardiac anxiety. Participants who were unable to view the education videos during enrollment will be able to do so during Visit 1.

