Participants will be excluded if they have any of the following: (1) severe disabling chronic medical and/or psychiatric comorbidities determined on a case-by-case basis that prevent safe or adequate participation; (2) deemed unable to comply with the protocol (either self-selected or indicated during screening that s/he/they could not complete all requested tasks). This includes, but is not limited to, patients with a level of cognitive impairment indicative of dementia, patients with current alcohol or substance abuse, and patients with severe mental illness (e.g., schizophrenia); (3) unavailable for follow-up for reasons such as terminal illness and imminent plans to leave the United States (as we have migrant or mobile patients due to their citizenship and work issues); (4) Non-English and non-Spanish speaking; (5) Lack of reliable phone or e-mail access; (6) History of bipolar disorder (manic episode can be triggered by BLT) or positive screen for bipolar disorder based on the Mood Disorder Questionnaire; (7) Eye disease including glaucoma or retinopathy (BLT contraindications); (8) Blindness; (9) Night shift work schedules; (10) taking any anti-depressant or anti-anxiety medications; (11) taking other medications that increase sensitivity to light (by self-report).

After agreeing to participate in the study, participants will complete questionnaires to determine eligibility and collect sociodemographic factors (including age, gender, race, ethnicity, height, weight, partner status, education, work history, phone number, internet access, and home/mailing address). Further questionnaires specific to this study eligibility for the sleep complaint will assess presence of insomnia symptoms and/or short sleep duration. Insomnia is determined with a positive screen on the Insomnia

Symptoms Questionnaire. Habitual short sleep duration is determined by asking participants if they have slept 6 hours or less per night on any nights during the past month and if so, how often. Choices will include don't know, never (0 times per week), rarely (less than 1 time per week), sometimes (1-2 times per month), frequently (3-4 times per week) and always (5-7 times per week). Those indicating a positive screen for insomnia or "frequent" or "always" experiencing habitual short sleep duration will be eligible. Participants will also complete the Mood Disorder Questionnaire to screen for bipolar disorder (a contraindication for BLT), which will be an exclusion criterion.

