After a participant's eligibility is confirmed, the research coordinator will schedule Visit 1 with the participant. Visit 1 can occur either via Zoom Video, telephone, or in person according to participant preference and in consideration of the current institution guidelines related to COVID-19 and social distancing. The research coordinator may provide study devices and materials (e.g., GENEActiv, BLT visor, BLB glasses, and device instructions) while they are still in the hospital, within the next 1-2 weeks post-discharge or at Visit 1 if in person. If Visit 1 is conducted remotely, study devices and materials will be sent to the participant's home address. Participants will view the educational videos (~5 minutes each in length) during the enrollment visit. Participants will also have the option of watching the educational videos at home if they have internet access.

Visit 1: A member of the research team (coordinator or PI) will meet with the participant via Zoom Video, in person, or over the phone to conduct a series of pre-intervention preparation components, which includes a set of baseline questionnaires on sleep, a questionnaire on PTSD symptoms, and a questionnaire on cardiac anxiety. They will then conduct the intervention setup. If participants were unable to watch the educational videos during the enrollment visit, they will have the opportunity to view the video during Visit 1.

Baseline Questionnaires (20 mins): Participants will complete a set of questionnaires to obtain the following measures: severity of insomnia symptoms (7-item Insomnia Severity Index, ISI), self-reported global sleep quality and sleep duration (9-item Pittsburgh Sleep Quality Index, PSQI), PTSD symptoms (17-item PTSD Checklist – Specific, PCL-5), cardiac anxiety symptoms (18-item Cardiac Anxiety Questionnaire, CAQ). Note: These assessments will be completed at baseline (i.e., before intervention begins), 4 weeks later at the end of the intervention period, and in participants who are in Phase B, 3 months after the end of the intervention period.

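### Phase B is randomised before the first ISI and PSQI, so the baseline for the Secondary Aim 1 change scores is post-randomisation and may follow disclosure of the arm

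*Protocol*

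**What the plan says.** Protocol section 2, Overview of Phase B Study Design, gives the steps in order. Under Screening and consent: "Participants will complete a screening questionnaire to collect demographics, contact information, and participant sleep quality and habits". Allocation, two to CC for each control, comes next: "After completing the screening questionnaire, Phase B participants will be randomized to either the CC intervention arm or sleep hygiene education control group". Both arms are then to see two short sleep-education videos, and the combined chronotherapy (CC) arm is to be taught to use the visor and glasses. The timing of that teaching is flexible: "Instructions on how to use the intervention devices will be offered in person during enrollment, over the phone, or online via Zoom". Visit 1/Baseline is scheduled as a separate contact: "During Visit 1, participants will complete a questionnaire battery on their sleep, PTSD symptoms, and cardiac anxiety".

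Protocol section 3, Study Procedures, describes the screening content: "Further questionnaires specific to this study eligibility for the sleep complaint will assess presence of insomnia symptoms and/or short sleep duration". The tools named there are the Insomnia Symptoms Questionnaire and a question on how often short nights occur. The ISI and PSQI first appear at Visit 1, and their timing is fixed relative to treatment, not to allocation: "These assessments will be completed at baseline (i.e., before intervention begins), 4 weeks later at the end of the intervention period". Study devices may be provided "while they are still in the hospital, within the next 1-2 weeks post-discharge or at Visit 1 if in person". For a remote Visit 1 they are mailed to the home.

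The SAP, Secondary Aim 1, lists three measures, each a within-person change from baseline: ISI total, PSQI total and the PSQI sleep-duration subscale. The aim is to see whether sleep changes more under CC than under control. The SAP plans to look at the change scores and the pattern of their means, and says that the trial is not powered to test them.

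**The concern.** A baseline taken before allocation cannot be influenced by allocation. Here the ISI and PSQI come after it, and neither document describes blinding or withholding the arm until the battery is done. A participant who knows that a light visor is coming, or that only education is coming, may rate the same sleep differently. Because each measure subtracts the Visit 1 score, such a shift would pass into the change score.

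The videos add a second, smaller issue. They and their written summary are the only education that the Protocol describes for the control arm, yet either arm may see them before Visit 1. The baseline may therefore already follow the control content.

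What is at stake is the reading of Secondary Aim 1, the only between-arm question in the plan.

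**Working it through.** **Order of Phase B steps, from Protocol sections 2 and 3**

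| Step | Content | Relative to allocation |
|---|---|---|
| Screening | Insomnia Symptoms Questionnaire, short-sleep frequency, bipolar screen | before |
| Randomisation | 2:1 | – |
| Videos | both arms; in hospital, at home, or at Visit 1 if not yet seen | after |
| CC device instruction | in person, by phone or by Zoom | after |
| Device provision | in hospital, within 1-2 weeks of discharge, at an in-person Visit 1, or by mail if remote | not stated; arm-specific for visor and glasses |
| Visit 1 | ISI and PSQI, then intervention set-up | after |
| Day after Visit 1 | device use starts | after |
| Visit 2 | 4 weeks after Visit 1 | after |

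**Does any passage reverse this order?** No. Section 3 schedules Visit 1 once eligibility is confirmed and places set-up after the questionnaires, but it does not mention randomisation. Screening covers sleep, but neither the ISI nor the PSQI is named there, so it cannot supply the starting value of a change score.

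**Size.** The plan gives no power figure for this aim to reproduce. From the Protocol, 15 participants at 2:1 gives 10 CC and 5 control. The rest is assumed: equal SD at both visits (the unit below); correlation ρ between visits of 0.5 or 0.7; a Visit 1 reporting shift d (CC minus control), illustrated at 0.2 and 0.5 SD; and a fraction k of it that persists to Visit 2.

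Standard error of the difference in mean change = √[2(1−ρ)(1/10 + 1/5)]
- ρ = 0.5: √(2 × 0.5 × 0.3) = √0.30 = 0.548 SD
- ρ = 0.7: √(2 × 0.3 × 0.3) = √0.18 = 0.424 SD

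Bias in the contrast as scheduled = kd − d, which is d(1−k) in size. With the battery before allocation, only the Visit 2 part, kd, remains.

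| k | As scheduled, d = 0.2 to 0.5 | In SE (ρ = 0.5) | In SE (ρ = 0.7) | Battery first |
|---|---|---|---|---|
| 0 | 0.20 to 0.50 SD | 0.37 to 0.91 | 0.47 to 1.18 | 0 |
| 0.5 | 0.10 to 0.25 SD | 0.18 to 0.46 | 0.24 to 0.59 | 0.10 to 0.25 SD |
| 1 | 0 | 0 | 0 | 0.20 to 0.50 SD |

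A simulation of 200,000 trials with no true effect, d = 0.5, k = 0 and ρ = 0.5 gave a bias of −0.499 SD and a standard error of 0.548 SD, in agreement with the formulas. The documents give no d, k or ρ, so the true bias may be zero.

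**The case against.** The strongest reply is that harm is conditional and the remedy only partial. Device instruction may come late, set-up follows the questionnaires within Visit 1, and the Recruitment and Enrollment section that the Protocol cites is not in the available text. Silence on disclosure is therefore weak evidence. This stands. A reader might infer from the order of the sentences that CC participants know their arm when they complete the battery; the documents permit that but do not establish it.

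It also stands that Visit 2 self-report remains open-label. As the table shows, moving the battery lowers the net bias in the change contrast only if less than half of the shift persists (k < 0.5); if all of it persists, the present order cancels it. But that cancellation rests on a persistence that the trial cannot verify. A pre-allocation baseline leaves one recognisable limitation, open-label self-report at Visit 2, instead of two that may or may not offset each other.

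Two stronger readings are not supported:
- A reader might infer that an earlier baseline would recover participants lost between randomisation and Visit 1. Visit 2 is timed from Visit 1, so someone who never reaches Visit 1 has no scheduled Visit 2 and no change score either way.
- A reader might bring in actigraphy, as rescue or as a further fault. Whether it has a usable baseline is a separate question, and the SAP does not list it among these measures.

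**Conclusion.** The point holds, as a minor one. The Phase B order is plain in the text: the ISI and PSQI baseline is post-randomisation. It precedes device use, so contamination by treatment is not the issue; the issue is possible influence of a known allocation and of the videos on self-report.

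Any resulting bias is of unknown size and direction, from zero upward. The only firm scale is the standard error of the contrast, about 0.55 SD for 10 v 5 at an assumed correlation of 0.5. The multiples of it shown above depend wholly on assumed d, k and ρ and are not estimates. The primary feasibility measures do not use this baseline, and the SAP names no between-arm test and disclaims power for the sleep outcomes.

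**What to change.** **Participants still to be enrolled in Phase B.** Amend Protocol section 2 (Phase B, Screening and consent; Visit 1/Baseline) and section 3 (scheduling of Visit 1; Baseline Questionnaires) so that the existing Visit 1 battery is completed once eligibility is confirmed, and before randomisation, the videos, and any arm-specific instruction, hand-over or mailing.
- In person: randomise at the end of the Visit 1 questionnaires.
- Remote: do the battery by phone or Zoom, then randomise and ship.
- Where devices would be given in hospital: hold the hand-over until the battery is done, or do the battery there first.

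Record the battery date, state which contact the four weeks to Visit 2 are counted from, and report the baseline-to-Visit 2 interval by arm.

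**Participants already enrolled.** Report that baseline followed randomisation, and compare the pre-randomisation screening sleep items by arm. These items check comparability; they cannot replace the ISI or PSQI. If Phase B enrolment is complete, only reporting applies.

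**In either case**, state that Visit 2 self-report is open-label, so reordering removes only the baseline part of any reporting bias.

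**Cost.** An amendment that reorders existing steps, with no new form or patient. Remote participants would have a somewhat longer and less uniform interval to Visit 2. A battery done in hospital would describe sleep closer to the coronary event. If Phase B is under way, as the Compensation section suggests, two baseline procedures would be mixed among 15 participants, so report who had which.

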of how the external light environment impacts sleep), the relationship of sleep with health, function, and well-being and tips for achieving good sleep. Participants will have the option of watching the educational videos during hospitalization or at home for those with internet access and participants will also be given a written summary of the contents of the educational videos.

Phase A participants will then be instructed on how to administer the CC intervention. The CC intervention will consist of a wearable light visor to administer the BLT each morning for 30 minutes after awakening, and the BLB glasses to be worn each night from 8:00pm to bedtime. Instructions on how to use the intervention devices will be offered in person during enrollment, over the phone, or online via Zoom after the participant has returned home.

Visit 1/Baseline: After verbally agreeing to participate and enroll in the study, Phase A participants will be scheduled for Visit 1 (either in person, telephone, or video on Zoom). During Visit 1, participants will complete a questionnaire battery on their sleep, PTSD symptoms, and cardiac anxiety. Participants who were unable to view the educational videos during enrollment will be able to do so during Visit 1.

Phase A participants will receive a wrist-mounted accelerometer (GENEActiv) designed to measure their sleep and physical activity. Coordinators will provide participants with the device and instruct participants to begin wearing it the day following Visit 1. They will be asked to wear this GENEActiv on their wrist for the next 4 weeks. Upon successful completion of Visit 1, Phase A participants will be asked to begin the intervention the following day, starting with BLT in the morning and BLB that night. Use of the intervention will continue daily for the next 4 weeks. Participants will also be asked to complete a paper-based sleep diary/daily-use log, where they will document the times they administered each of the interventions (i.e., time of starting and stopping BLT, time of donning and doffing BLB glasses, and times of going to bed and waking up). Research staff will contact participants weekly to collect the data that were entered in the sleep diary/daily use log, and also to ask about any adverse events or side effects (see below).

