Phase B participants will receive a wrist-mounted accelerometer (GENEActiv) designed to measure their sleep and physical activity. Coordinators will provide participants with the device and instruct participants to begin wearing it the day following Visit 1. They will be asked to wear this GENEActiv on their wrist for the next 4 weeks. Upon successful completion of Visit 1, Phase B participants randomized to the active CC intervention will be asked to begin the intervention the following day, starting with BLT in the morning and BLB that night. Use of the intervention will continue daily for the next 4 weeks. Participants will also

be asked to complete a paper-based sleep diary/daily-use log, where they will document the times they administered each of the interventions (i.e., time of starting and stopping BLT, time of donning and doffing BLB glasses, and times of going to bed and waking up). Phase B participants randomized to the sleep hygiene education control arm will also be asked to wear a GENEActiv for 4 weeks and complete the sleep diary (indicating times of going to bed and waking up) each day. Research staff will contact all Phase B participants weekly to collect the data that were entered in the sleep diary/daily use log, and also ask the participants randomized to the active CC intervention about any adverse events or side effects (see below).

After enrollment, participants will be provided with a pre-paid package which can be used to return the BLT visor, GENEActiv, the sleep diary/daily use log, and the exit interview at the conclusion of Visit 2.

Visit 2: At the end of the intervention period (4 weeks after Visit 1), all Phase B participants (intervention and control arm) will complete Visit 2 in person, over the phone or via Zoom. During Visit 2, participants will complete measures of sleep quality, cardiac anxiety, and PTSD symptoms. Additionally, participants in the active CC intervention group will complete questionnaires about feasibility, acceptability, appropriateness, and usability of the intervention.

Phase B participants will be provided with a pre-paid envelope which can be used to return the study devices, the exit interview, and the sleep diary/daily use log after Visit 2. If the exit interview is not returned, research staff may call the participant to administer the questionnaire over the phone (though this has no bearing on participant compensation).

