Between Visit 1 and Visit 2: For the 4 weeks between Visit 1 and Visit 2, participants in Phase A and participants in the active CC arm group of Phase B, will be instructed to wear the BLT visor for 30 minutes each morning starting after awakening, and to record the time they put them on and remove them each day in their sleep diary/use log. These participants will also be instructed to wear their BLB glasses beginning at 8:00PM each night until they go to sleep, and to record the time they put them on and remove them each day in their sleep diary/use log. Participants will also wear the glasses during any nocturnal awakenings in which a light is turned on, a light-emitting electronic device is used in bed, etc. All participants (in both arms) will also be instructed to record in their sleep diary/use log when they go to sleep and wake up each day. There will be weekly check-ins via telephone call by the research team to remind participants to use the devices and continue to complete the sleep diary/use log. During the check-ins, research staff will collect the data that has been entered in the sleep diary/use log. Additionally, research staff will ask on a weekly basis during the check-in call if the participant has experienced any adverse events or side effects. The research staff will ask "Over the past week, have you experienced any side effects from either of the treatments? If so, please tell us what you experienced. If possible, please tell us which portion of the intervention (light visor or orange-tinted glasses) you believe may have caused this side effect." Any reported adverse events or side effects will be reported to the study PI ([name]), the study physician ([name]) and the study safety officer ([name]).

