Please note, participants who are determined to be ineligible at any time during the screening questionnaire will not be compensated.

Please note, due to the change in vendor for Columbia University PayCards, current and past participants of both Phase A and Phase B who receive(d) a Bank of America PayCard, will receive a PayCard addendum letter by email and/or mail to ensure they are aware of the card expiration date.

4. Risks

Bright light therapy (BLT): Although extremely unlikely, participants may encounter risks that any person may encounter when engaging in treatment with BLT. BLT side effects can rarely include eye strain, headache, nausea, irritability or agitation. These side-effects are expected to be mild, and to be reversible with cessation of therapy.

Participants are encouraged to stop or reduce their use of light therapy if they experience any side-effect that they perceive as severe. A study physician and a sleep expert (the study PI) will be available by email for questions about side-effects during business hours and participants will also be able to contact

their personal physicians as they would in clinical practice if any questions pertaining to study light therapy arise. Research coordinators will review phone calls and emails at least twice per day and will relay any questions that could relate to patient safety to the study physicians. The presence of adverse events or side effects related to treatment will be assessed on a weekly basis, via phone calls made to participants by research staff.

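### On the most coherent reading, the weekly Phase B adverse-event question goes only to the CC arm and covers only effects attributed to treatment, so safety prompting is not comparable between arms

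*Protocol*

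**What the plan says.** **Who is called and who is asked.** In Protocol section 2, Overview of Phase B Study Design, Visit 1/Baseline: "Research staff will contact all Phase B participants weekly to collect the data" from the diary. The same sentence goes on to say that staff will "also ask the participants randomized to the active CC intervention about any adverse events or side effects", and ends by pointing to text further on.

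**The procedure itself.** That text is in Protocol section 3, Between Visit 1 and Visit 2. The paragraph addresses both arms for the diary: "All participants (in both arms) will also be instructed to record in their sleep diary/use log". It then says that staff will ask each week "if the participant has experienced any adverse events or side effects", with no arm named. The question given word for word is narrower: "Over the past week, have you experienced any side effects from either of the treatments". Its follow-up asks, where possible, which device was responsible, and names only the visor and the tinted glasses.

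**The risk section.** Protocol section 4, under bright light therapy: "The presence of adverse events or side effects related to treatment will be assessed on a weekly basis", by phone, again with no arm named.

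**Phase A.** The Phase A overview uses the broad wording: "and also to ask about any adverse events or side effects (see below"). Everyone in Phase A had the devices.

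**Other routes.** Section 4 says that coordinators check calls and emails no fewer than two times a day and pass safety-related questions to study physicians, that a study physician and the principal investigator can be emailed, and that participants may turn to their own doctors. Section 3 sends any event that is reported to the principal investigator, study physician and safety officer. There is also an exit interview, whose content is not given: "If the exit interview is not returned, research staff may call the participant to administer the questionnaire over the phone".

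**SAP.** Neither the aims nor the General Approach lists an adverse-event summary.

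**The concern.** Controls are phoned every week but, as the Phase B overview reads, are not asked about adverse events. CC participants are asked, but the scripted question already contains a causal judgement: it invites a report only if the participant believes that a treatment caused the effect.

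Participants are within 3 months of an acute coronary syndrome, and the listed effects of bright light (such as headache, nausea and agitation) are non-specific. Without the same open question in both arms, there is no background rate against which to read CC reports. A CC event that the participant puts down to the heart condition or its drugs may not reach the people whose task is to judge causality. What is at stake is the completeness and comparability of the safety record of a pilot, not its feasibility or sleep results.

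**Working it through.** The plan states no figure on this point, so there is none to reproduce. The check sets the passages side by side and then counts.

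**1. Side by side.**

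| Place in Protocol | Who is asked | What is asked |
|---|---|---|
| Section 2, Phase B overview | CC arm only | any event |
| Section 3, lead-in | arm not stated | any event |
| Section 3, script | makes sense for device users only | effects of the treatments |
| Section 4, bright light therapy | arm not stated | treatment-related events |

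On *who*, three things favour CC only: the overview says so and points forward to the procedure, the script names only devices that controls do not have, and the same section 3 paragraph says that the calls serve to remind participants to use the devices without limiting that to the CC arm. Its unqualified reference to the participant is thus weak evidence of an all-arm rule. On *what*, the text divides: the overviews and the lead-in are broad, while the script and section 4 are narrow.

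**2. Participants and calls not prompted.** Inputs: 15 randomized 2:1 (section 2); 4 weeks between visits (section 3); four calls each with no dropout (assumption).
- CC: 15 × 2/3 = 10. Control: 15 × 1/3 = 5.
- Calls: 15 × 4 = 60, of which CC 10 × 4 = 40 and control 5 × 4 = 20.
- With no adverse-event question: 5/15 = 33% of participants, 20/60 = 33% of calls.
- The 40 CC calls do include a question. If staff use the script alone, it is limited to effects attributed to treatment.

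**3. Could there be anything to miss?** The documents give no event rate. For an assumed 4-week risk p per person, the chance of at least one event among the 5 controls is 1 − (1 − p)^5: 23%, 41%, 67% and 83% for p = 5%, 10%, 20% and 30%. This is the chance that an event occurs, not that it goes unrecorded.

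**4. What by-arm data could show after a fix.** With zero events in n participants, the exact two-sided 95% upper limit is 1 − 0.025^(1/n).
- Best case, nobody yet called under the existing script: 0/5 gives 1 − 0.025^(1/5) = 52%; 0/10 gives 1 − 0.025^(1/10) = 31%.
- If 3 of 15 are already through (assumption), about 8 CC and 4 control remain: 37% and 60%.
- If 8 of 15 are already through (assumption), about 5 CC and 2 control remain: 52% and 84%.

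**The case against.** The strongest reply is that asking only device users about device effects is a coherent design choice in a small pilot with low expected harm. By the Protocol's own account, earlier pilots had no reported adverse events, night-time use of the lenses carries no known risk, and falls are unlikely. Safety is not among the aims, so the SAP breaks no commitment by omitting it. Participants can report anything by phone or email, and any report is forwarded. Five controls cannot support a comparison. The public text may also be partial: the Protocol refers to a recruitment and enrollment section that is not in the file.

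Much of this stands, and it is why the point is minor. It does not remove the gap. The unsolicited routes narrow it but do not put the same question to both arms, and calling the rule a choice does not explain why the lead-in promises more than the script delivers.

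Some stronger readings are tempting but not supported:
- *That the Protocol flatly contradicts itself on who is asked.* The forward pointer and the device-only script let the passages be read as one CC-only rule. They are loosely worded rather than clearly opposed.
- *That the script is a lone slip.* Section 4 uses the same narrow scope.
- *That none of the 60 calls carries an attribution-free question.* This treats the script as the whole inquiry despite its broad lead-in, and the documents do not say that it is.
- *That control events are lost.* Not prompted is not the same as not reportable, and the exit interview may ask.

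**Conclusion.** The point holds, as a minor one. On the most coherent reading, 5 of 15 randomized participants (about 20 of 60 calls, assuming four each and no dropout) get no adverse-event question, and the script does not prompt CC participants for events they do not attribute to a device. The consequence is uneven prompting and a safety record that cannot be compared between arms. The documents do not allow an estimate of how many events would be missed.

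Confidence is high that the script is narrower than its lead-in. It is lower on who is meant to be asked, because the text can be read as a single CC-only rule. The statement that there is only one script applies to the public text.

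**What to change.** Reconcile the Phase B overview in section 2, the lead-in and script in section 3, and the wording in section 4, so that they state who is asked and what is asked. Open each remaining weekly call in both arms, in English or Spanish, with the same attribution-free question on any new symptoms or medical problems. Follow it with the existing device question in the CC arm only. A checklist of expected effects is not needed; since participants know whether they have devices, it could invite expectation-driven reports in the CC arm.

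Add one line to the SAP: counts by arm from the common question, descriptive and without a test; device-attributed effects listed separately for the CC arm; calls made before the script change shown separately.

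Cost: no new calls, since controls are already phoned. At an assumed 1 to 2 minutes per call, the most it could take is 60 × 1 to 60 × 2 = 60 to 120 minutes in all, or 4 to 8 minutes per participant. It needs a short script amendment and Spanish wording, and will bring more unrelated events to log and review. The Compensation section refers to current and past participants of both phases, so Phase B may be under way and ascertainment would then be mixed: if 3 or 8 of 15 are through (assumption), 12 or 32 of the 60 calls (20% or 53%) used the existing script. Phase A follow-up is complete, so its 5 × 4 = 20 calls cannot be changed.
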